23.2 Fonts

The font type "Arial", "Courier", "Courier New" or "Times New Roman" must be used for tables, listings and figures, with a font size of minimum 9 and it should be consistent for the whole report. The font color must be black for tables, listings and figures.

Colors are allowed for figures as long as the data series can be distinguished clearly if printed in black and white paper.

23.3 Header and Footer Information

Headers and Footer should be defined as follows:

- The header should be placed at the top of the page (same place on each page).
- Prop case should be used for titles and column names in header.
- Titles should not contain quotation marks or footnote references.
- The sponsor name should appear in left-aligned, the purpose of the analysis indicated in SAP in center aligned in row 1 of header.

- The protocol number should appear in left-aligned, if available cutoff date in SAP in center aligned in row 2 of header.
- The TLF identification number should appear in row 3, centered in header.
- The TLF title should start in row 4, centered in header.
- The TLF population should appear in row 5, centered in header. The population will be spelled out in full, e.g. Safety analysis population in preference to Safety analysis population.
- Row 6 in header should be a continuous row of underscores ('_') (the number of underscores should equal the line size).
- The column headings should be underlined with a row of underscores ('_').
- Column headings spanning more than one column should be underlined and have underscores on either side of the title and should be centered.
- In general, the analysis population count should appear in the column header in the form "(N=XX)" and column headings containing numbers should be centered.
- The page footnotes should provide the following information: the source (ADAM dataset with timestamp as date time, SDTM dataset with timestamp as date if applicable), the program (Program name with timestamp as date time) in two lines left aligned with a separation solid line above.
- The word "CONFIDENTIAL" should appear in row 1, centered aligned at footer in compiled file only.
- The page identification in the format Page X of Y (where Y is the total number of pages for the TLF) should appear in row 2, right aligned at Footer for compiled TLFs if required.

23.4 Table and Data Listing Table, Listing and Figure (TLF) Conventions

23.4.1 General

- The first row in the body of the table or data listing will be blank.
- The left-hand column should start in Column 1.
- Rounding will be done with the SAS® function ROUND if applicable.
- Numerical values in tables should be rounded and not truncated as per section (23.4.2.1) for respective statistics.
- Numerical values will be center aligned.

- Text values should be left aligned.
- The first letter of a text entry should be capitalized.
- The study drug will be appeared first in tables with treatment group as columns.
- The width of the TLF should match the line size.

23.4.2 Univariate statistics

23.4.2.1 Continuous variables statistics

- Statistics should be presented in the same order across tables (i.e., n, mean, SD, SE, IQR, minimum, median and maximum).
- If the original data has N decimal places, then the summary statistics should have the following decimal places:
 - Minimum, maximum: N.
 - CV (%): N+2.
 - Mean and median: N +1.
 - o SD: N + 2.
 - o SE: N+2.
 - IQR: N+2.

23.4.2.2 Categorical variables statistics (Frequencies and percentages [n and %])

- The percentages should be reported inside parentheses, with one space between the count and the left parenthesis of the percentages. An example is given below:
 - o **124 (645)**
- Percentages will be reported to one decimal place, except percentages <100.0 but >99.9 will be presented as '>99.9' (e.g., 99.99 is presented as >99.9); and percentages <0.1 will be presented as '<0.1' (e.g., 0.08 is presented as <0.1). Rounding will be applied after the <0.1 and >99.9 rule.
 - o (<0.1)
 - o (6.8)
 - o (>99.9)
- Percentages may be reported to 0 decimal places as appropriate (for example, where the denominator is relatively small).

Page 81 of 85

• Where counts are zero, then counts and percentages will be represented as "0 (0.0)" respectively in the table.

23.4.3 Confidence intervals (CIs)

- Cls should be presented with one additional decimal place as that of the raw data.
- Cls will be presented as (lower bound, upper bound).

23.4.4 P-values

P-values should be reported to four decimal places.

23.4.5 Ratios

 Ratios should be reported with one additional decimal place as that of the raw data.

23.4.6 Spacing

There should be a minimum of 1 blank space between columns (preferably 2).

23.4.7 Missing values

- A "0" should be used to indicate a zero frequency.
- A blank will be used to indicate missing data in data listings.

23.5 Tables, Listings and Figure output conventions

The compiled final file will be presented in PDF format with TOC for listing and table/figures separately. The Table, Listing and Figures will be provided in RTF (if requested form sponsor) and PDF files using the SAS[®] Output Delivery System (ODS).

All percentages (%) for a specific summary are calculated using the total number of participants included in the relevant analysis population as the denominator, unless otherwise specified.

Data listings will be based on all participants treated, unless otherwise specified.

By default, descriptive statistics for quantitative measurements will include the number of participants (n), mean, standard deviation (SD), minimum, median and maximum

23.6 Dates and times

In footer of the TLFs date and time will be presented in format ddMMMyyyy and hh: mm.

23.7 Spelling format

The spelling format to be used is English US.

23.8 Presentation of treatment groups

This study is single arm so, we have only one treatment group i.e. Basaglar.

23.9 Presentation of visits

- Visit 1 (Week -2)
- Visit 2 (Week 0)
- Visit 3 (Week 4)
- Visit 4 (Week 8)
- Visit 5 (Week 12)
- Visit 6 (Week 16)
- Visit 7 (Week 20)
- Visit 8 (Week 24)
- Visit 9 (Week 28)

24. Appendix 2: Partial date conventions for adverse events.

The whole missing date will not be imputed for this study and only partial date imputation will be performed. Conventions pertaining to partial dates are presented in Table 24.1.

| Table 24.1: Algorithm for Partial Date I | mputation of Adverse Event |
|--|----------------------------|
|--|----------------------------|

| ADVERSE EVENT | MISSING | IMPUTATION |
|---------------|---------------------|--|
| Start Date | Day | If AE start month = Treatment start month and AE start year = Treatment start year, then AE start day= Treatment start day Otherwise AE start day=01 |
| | Day and Month | If AE start year = Treatment start year, then AE start day and month = Treatment start day and month Otherwise AE start day = 01 and AE start month=Jan |
| | Day, Month and Year | No imputation will be performed |
| End Date | Day | If AE end month = Date of study completion/discontinuation month and AE end year = Date of completion/discontinuation year, then AE end day = date of completion/discontinuation day Otherwise AE End day = Last day of respective month, used if this does not result in a date after the subject's trial exit date (e.g. death) in which case the trial exit date will be used |
| | Day and Month | If AE end year = Date of study completion/discontinuation year, then |

CONFIDENTIAL CS.BS.01.00 TPL-1.0: Statistical Analysis Plan Template

Page 84 of 85

AE End day and month = Date of study completion/discontinuation day and month Otherwise AE end day = Last day of respective month and AE end month = Last month of the year, used if this does not result in a date after the subject's trial exit date (e.g. death) in which case the trial exit date will be used

Day, Month and Year No imputation will be performed

CONFIDENTIAL CS.BS.01.00 TPL-1.0: Statistical Analysis Plan Template

Page 85 of 85

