16.1 Variables and derivations

Adverse Events (AEs) will be coded using MedDRA central coding dictionary, Version (refer to DMP for dictionary version).

Adverse events (AE) and Serious adverse event (SAE) are defined as events that are reported after the signing the inform consent form (ICF).

Treatment-emergent adverse events (TEAEs) are defined as events that are newly reported after the first study drug treatment or are reported to have worsened in severity after the first study drug treatment. In the case where it is impossible to define an AE as treatment-emergent or not, the AE will be classified by the worst case assigned, i.e. a TEAE.

In section 24 Appendix 2 the algorithm is given for calculation of partial date imputation for adverse events (AEs) and it will be used for partially missing adverse event start and end date imputation.

Each adverse event will be described by following in listing:

- Subject Number
- Description (AE term) i.e. System organ class/ Preferred terms / Reported terms
- Duration (start and end dates)
- Severity of event
- Relationship to the investigational product
- Relationship to non-study drug treatment
- Relationship to the study procedure
- Action taken with the study treatment
- Outcome
- Whether SAE or not

Each serious adverse event will be described by following in listing:

Subject Number

CONFIDENTIAL CS.BS.01.00 TPL-1.0: Statistical Analysis Plan Template Page 41 of 85

- Description (SAE term) i.e. System organ class/ Preferred terms / Reported terms
- Duration (start and end dates)
- Seriousness criteria
- Toxicity grade
- Severity
- Causality
- Outcome

The following parameters will be summarised for the subject's adverse events as mentioned in eCRF

- Number of participants with at least one TEAEs
- Number of participants with at least one drug related TEAEs
- Number of participants with at least one serious TEAEs
- Number of participants with at least one drug related serious TEAEs
- TEAE by Severity
- TEAEs leading to Death
- Drug-related TEAEs leading to Death
- TEAEs leading to early withdrawn of study
- Injection site Adverse events

Derivations:

- If adverse event start date ≥ Study drug administration start date, then we will consider it as TEAE.
- If adverse event start date ≥ Study drug administration start date and adverse event related to study treatment = "YES", then we will consider it as drug related TEAEs.

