20.1 Variables and derivations

20.1.1 Serious adverse events (SAEs) and treatment-emergent adverse events (TEAEs)

Variables:

- First Study drug administration Date
- Serious AE start Date
- Inform consent date
- Adverse Event Serious i.e. (AESER)

Derivations:

- If Adverse Event Serious i.e. (AESER) = "YES" and Serious AE start Date >= Inform consent date, then we will consider it as serious adverse event (SAE)
- If AE start Date >= First Study drug administration date, then we will consider it as treatment-emergent adverse events (TEAEs)

20.1.2 Rates per 30 days and per subject year of total hypoglycemic events (symptomatic or asymptomatic)

Variables:

- What was the blood glucose level (mg/dL) prior to treating the event? (In eCRF "Hypoglycemia Events" form)
- Were signs/symptoms of hypoglycemia present, other than the blood glucose reading? (In eCRF "Hypoglycemia Events" form)
- Hypoglycemic event start date
- Date of Visit 2 (Week 0)
- Date of Visit 8 (Week 24)
- Date of Visit 9 (Week 28)
- Date of first IMP dose administration (In eCRF "Exposure" form)
- Date of last IMP administration (In eCRF "End of Study" form)

Derivations:

- The symptomatic and asymptomatic i.e. total hypoglycemic events will be identified based on derivation mentioned in section 19.1.1.
- Hypoglycemic event start date ≥ Date of Visit 2 (Week 0) and Hypoglycemic event start date ≤ Date of Visit 8 (Week 24) for accessing the hypoglycemic events from Day 0 to week 24.
- Hypoglycemic event start date ≥ Date of Visit 2 (Week 0) and Hypoglycemic event start date ≤ Date of Visit 9 (Week 28) for accessing the hypoglycemic events from Day 0 to week 28.

The formula used for calculation for rates per 30 days and per subject year (365.25 days) of total hypoglycemic events mentioned below:

The rate of hypoglycemic events per 30 days $= \frac{\text{"The total number of events between the time points"}}{\text{"Actual number of days between the time points"}} * 30$ The rate of hypoglycemic events per year (365.25 days) $= \frac{\text{"The total number of events between the time points"}}{\text{"Actual number of days between the time points"}} * 365.25$ Offset variable for per 30 $= log \left(\frac{\text{"The Duration of treatment exposure"}}{30}\right)$ Offset variable per year $= log \left(\frac{\text{"The Duration of treatment exposure"}}{365.25}\right)$

Note: For the duration of treatment exposure see formula mentioned in section 12.1

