20.2 Analyses

- 20.2.1 Serious adverse events (SAEs) and treatment-emergent adverse events (TEAEs)
 - Population: FAS and PPS Stratification: Table: NA Listing: NA Statistics: The SAE and TEAE will be identified by using derivation mentioned in section 20.1.1. Summary statistics for SAEs and TEAEs will be presented as frequency and percentage (n and %) for table.

20.2.2 Rates per 30 days and per subject year of total hypoglycemic events (symptomatic or asymptomatic)

| Population: | FAS and PPS |
|-------------|-------------|
|-------------|-------------|

Stratification: Table: NA

Listing: NA

Statistics: The rate that is the number of hypoglycemic events per subject over the study period i.e. Day 0 to week 24/week 28 will be summarised as continuous variables as (n, mean, standard deviation, standard error, median, minimum, maximum).

> By using the formula mentioned in section 20.1.2, we will get the Rates per 30 days and per subject year (365.25 days) between two time points (i.e. baseline to end of treatment/study) and This Rates per 30 days and per subject year (365.25 days) will be summarised as (n, mean, standard deviation, standard error, median, minimum, maximum).

> Summary statistics and efficacy table will be presented separately for baseline to end of treatment and baseline to end of the study.

Page 63 of 85

The Negative Binomial Model without categorical variable i.e. the generalized linear model will be used with HbA1c as covariate and the log of the study treatment exposure time as offset variable.

The estimate, 95% confidence interval and p-value will be provided for efficacy table.

The Negative binomial regression equation is as follows:

Y = Offset variable + α + β (X)

Where,

Y= The response rate of 30 days and per subject year for total hypoglycaemic events.

Offset variable = The log of study treatment exposure time for rates per 30 days and per subject year (See section 20.1.2 for formula)

 $\alpha = Intercept$

 β =slope

X= Covariate i.e. Baseline HbA1c results

The hypothesis is as follows

H0: $\beta = 0$

i.e. The Rate of per 30 days and per subject year of total hypoglycaemic events not significantly differs depending on the Baseline HbA1c..

V/s

H1: β ≠ 0

i.e. The Rate of per 30 days and per subject year of total hypoglycaemic events significantly differs depending on the Baseline HbA1c. events.

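### SAP Table 24.1 imputes AE start dates without using end or consent dates, so in treated subjects some events known to precede first dose become TEAEs and some screening SAEs miss the 20.2.1 table

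*SAP*

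**What the plan says.** The imputation rule is in SAP Section 24, Appendix 2, Table 24.1 (Start Date rows).

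- Day missing: if month and year match treatment start, "then AE start day= Treatment start day Otherwise AE start day=01".
- Day and month missing, with a matching year: "If AE start year = Treatment start year, then AE start day and month = Treatment start day and month".
- For any other year, the fallback is 1 January of the reported year: "Otherwise AE start day = 01 and AE start month=Jan".

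The start-date rows contain no check against the event's end date or the consent date. The end-date rows do carry a guard, since an imputed end may not pass the trial exit date.

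SAP 16.1 applies the table to adverse events: "it will be used for partially missing adverse event start and end date imputation". It then classifies on the start date alone: "If adverse event start date ≥ Study drug administration start date, then we will consider it as TEAE". The derivations in 16.1 for drug-related and serious TEAEs, and for TEAEs leading to death or withdrawal, repeat the same start-date test, and 20.1.1 uses it for TEAEs as well. The worst-case rule in 16.1 is conditional: "In the case where it is impossible to define an AE as treatment-emergent or not, the AE will be classified by the worst case". Under that rule, such an event counts as treatment-emergent.

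SAEs are defined twice. SAP 16.1 goes by reporting after consent and sets no start-date condition. SAP 20.1.1 requires the serious flag and a start on or after consent: "Serious AE start Date >= Inform consent date, then we will consider it as serious adverse event (SAE". The endpoint table follows the second definition: "The SAE and TEAE will be identified by using derivation mentioned in section 20.1.1" (20.2.1).

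**The concern.** Protocol 9.2.1 has every adverse event after consent recorded and assessed for seriousness, so screening-period events belong in the data. For such an event with a partial start date, the rule can overlook two facts the database already holds: when the event ended and when the subject consented.

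Two errors can follow. An event that was over before the first injection can be tabulated as treatment-emergent, and the derived TEAE categories inherit the error. In the other direction, a serious event reported after consent can be dated to before consent and drop out of the SAE endpoint table. SAEs and TEAEs are a named secondary endpoint of a single-arm safety study, and the second error is not conservative.

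**Working it through.** The plan gives no figure on this point, so the check applies Table 24.1 literally.

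**Inputs.** Screening is 2 weeks (SAP 4.1) and Visit 2 has a window of ±3 days (SAP Table 7.1). Assuming consent at Visit 1 and first dose at Visit 2, the interval L from consent to first dose is 11 to 17 days. AE tables use FAS and PPS, so every analysed subject has a first-dose date.

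**Worked cases.**

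| Case | Consent | First dose | Recorded start | Recorded end | Imputed start | Consequence |
|---|---|---|---|---|---|---|
| A | 5 Mar 2020 | 19 Mar 2020 | Mar 2020 | 10 Mar 2020 | 19 Mar 2020 | 9 days after its own end; TEAE |
| B | 25 Mar 2020 | 8 Apr 2020 | 2020 | Mar 2020 | 8 Apr 2020 | Over by 31 Mar at the latest; TEAE |
| C (serious) | 25 Mar 2020 | 8 Apr 2020 | Mar 2020 | any | 1 Mar 2020 | 24 days before consent; fails 20.1.1 |
| D (serious) | 25 Dec 2019 | 8 Jan 2020 | 2019 | any | 1 Jan 2019 | Before consent; fails 20.1.1 |

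In A and B the end date settles that the event was not treatment-emergent. The worst-case rule in 16.1 therefore does not apply, and Table 24.1 gives a result contrary to it. In C and D the event is an SAE under 16.1 and not under 20.1.1.

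**Where the rule sends dates.** With L of 27 days or less, a screening event lies either in the first-dose month (set to first dose) or in an earlier consent month (set to day 01). Day 01 falls inside screening only if consent was itself on day 01 and first dose was in a later month, which needs at least 28 days (1 Feb to 1 Mar).

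Take every consent date in 2019–2022 (1,461 days, 48 month ends) and every screening day as the true start:

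- Combinations for one L: 1,461 × L. At L = 14: 1,461 × 14 = 20,454.
- Sent to before consent, day missing: 48 × L(L+1)/2. At L = 14: 48 × 105 = 5,040, or 5,040/20,454 = 24.6%. The other 15,414 (75.4%) go to first dose.
- L = 11 to 17 together: 1,461 × 98 = 143,178 combinations. Before consent: 48 × 749 = 35,952 (25.1%). First dose: 107,226 (74.9%). Inside screening: 0.
- Day and month missing, with 4 year ends: at L = 14, 4 × 105 = 420 (2.1%) go to before consent. For L = 11 to 17, 4 × 749 = 2,996 (2.1%) do. The rest go to first dose.

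**The case against.** The strongest reply is that imputing to first dose is deliberate. When only the month is known and no end date separates the event from treatment, calling it a TEAE is the conservative choice that 16.1 prescribes. That stands, and it removes one tempting inference: a reader might take the 75% as a rate of false TEAEs. It mixes intended worst-case classifications with the defect. The defective part is the subset with an end known to precede first dose, and the documents give no basis for sizing it.

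Second, a reader might infer that an SAE moved to before consent vanishes from all SAE reporting. It does not. The 16.1 definition keeps it, 16.2.9 has a separate serious-AE summary and listing, and protocol 10.3.2.4 lists all SAEs without a date filter. What is shown is a loss from the 20.2.1 table and a conflict between two definitions. A non-serious event moved to before consent is still correctly outside the TEAE tables.

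Third, the rule does not misplace every partially dated screening event. Never-treated subjects have no first-dose date, and for them the fallback branch can give a date on or after consent (about 25% of day-missing cases over 14 days). They are outside FAS and PPS. Screening of 28 days or more also breaks the pattern.

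Fourth, the practical weight is low. The window is about two weeks, AE review takes place at Visit 2 so recall is short, and knowing only the year of so recent an event would be unusual. The primary endpoint uses hypoglycemia-form dates and is untouched. All of this stands. It limits the size of the problem but does not make the rule right for cases A to D.

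**Conclusion.** The rule gives a wrong result in two defined situations among treated subjects:

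1. The event has a partial start in the first-dose month (or year) and a known end before first dose. It is dated after its own end and counted as a TEAE, against the SAP's own limit on worst-case classification.
2. The event is serious and its partial start is in a consent month (or year) that precedes the first-dose month (or year). It is dated before consent and lost from the 20.2.1 SAE table, while 16.1 still counts it.

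The number of affected events is unknown and probably small. The percentages assume evenly spread consent dates and event days, and only illustrate the split. The conclusion assumes that imputed dates feed the 20.1.1 tests, which is how 16.1 describes their use.

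**What to change.** Amend the start-date rows of Table 24.1 and the matching AE dataset code:

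- **(a) End-date condition.** If the known end date, or the latest date consistent with a partial end date, is before first dose, do not impute the start to first dose. Use the later of the first day of the reported period and the consent date, and do not classify the event as a TEAE.
- **(b) Consent floor.** Where the partial start is compatible with onset on or after consent, impute no earlier than the consent date. Limit the floor to those events, because an onset recorded as before consent should not be moved.
- **Definition.** Align the SAE derivation in 20.1.1 with 16.1, so that one definition feeds both 16.2.9 and 20.2.1.

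Keep imputation to first dose for events that are truly ambiguous. The worked cases then become: A, later of 1 Mar and 5 Mar = 5 Mar 2020; B, later of 1 Jan and 25 Mar = 25 Mar 2020; C, later of 1 Mar and 25 Mar = 25 Mar 2020; D, later of 1 Jan and 25 Dec = 25 Dec 2019. All four lie inside screening, none is a TEAE, and C and D count as SAEs.

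The cost is two programming conditions and one aligned sentence in the SAP. No new data and no protocol change are needed.
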